5. STUDY POPULATION

5.1. Inclusion Criteria

Patients must meet all the following criteria to be eligible for the study:

All Cohorts

1. Patient has voluntarily agreed to participate by signing an informed consent
2. Male or female and ≥ 18 years of age at the time of informed consent
3. Eastern Cooperative Oncology Group (ECOG) performance status of ≤ 1
4. Ability to swallow whole capsules
5. Patients who have histologic or cytologic-confirmed malignancy that has progressed to the advanced or metastatic stage
6. Agree to provide archival tumor tissue
 - a. **Dose Escalation Phase:** If available, agreement to provide archival tumor tissue for exploratory biomarker analyses
Note: If archival tumor tissue is not available, an optional fresh biopsy is highly recommended.
 - b. **Dose Expansion Phase:** patients enrolled in the HRD+ cohorts must provide archival tissue or fresh biopsy (if archival tissue is not available) for prospective central assessment of HRD status. Other cohorts may provide tissue, if available, for retrospective analysis.
7. Patients must have adequate organ function as indicated by the following screening laboratory values (obtained ≤ 2 weeks prior to Day 1):
 - a. Absolute neutrophil count (ANC) $\geq 1.5 \times 10^9/L$
 - b. Platelets $\geq 100 \times 10^9/L$ (Note: Criterion must be met without a transfusion within the 2 weeks prior to obtaining the sample)
 - c. Hemoglobin ≥ 10 g/dL or ≥ 6.1 mmol/L (Note: Criterion must be met without a transfusion within the 2 weeks prior to obtaining the sample)
 - d. Serum creatinine ≤ 1.5 x upper limit of normal (ULN) or estimated creatinine clearance ≥ 50 mL/min (calculated using the institutional standard method)
 - e. Total serum bilirubin ≤ 1.5 x ULN (total bilirubin must be < 4 x ULN for patients with Gilbert's syndrome or if indirect bilirubin concentrations are suggestive of extrahepatic source of elevation)
 - f. Aspartate and alanine aminotransferase (AST and ALT, respectively) ≤ 3 x ULN OR ≤ 5 x ULN for patients with liver metastases
8. Female patients of childbearing potential and female partners of male study patients must agree to practice highly effective methods of birth control ([Appendix 2](#)) for the duration of the study and for ≥ 6 months after the last dose of study drug. In addition, non-sterile male patients must agree to practice highly effective methods of birth control ([Appendix 2](#)) and avoid sperm donation for the duration of the study and for ≥ 6 months after the last dose of study drug.

9. Willingness and ability to comply with all protocol-specified requirements

Dose Escalation Phase only

10. Patient must have disease that is either measurable or evaluable per RECIST v1.1 criteria.

Dose Expansion Phase only

11. Patient must have measurable disease per RECIST v1.1 criteria (except where noted below).

Note: tumor lesions used for freshly acquired biopsies should not be included as target lesions unless there are no other suitable target lesions available

12. Ovarian Cancer (Expansion Cohort 1)

- a. Patients must have received at least one line of platinum-containing therapy in the advanced or metastatic setting.
- b. Patients must not have progressed or have recurrent disease within 6 months of the completion of the last platinum-containing regimen.
 - Note: Patients can receive additional therapy after the last platinum-containing regimen as long as the criteria for platinum-sensitivity is met.
- c. Patients with known or suspected deleterious mutations in BRCA1 or BRCA2 HRD+, regardless of the molecular signature result.
 - If HRD or BRCA1/2 mutation status is unknown or has not been previously evaluated, the patient must undergo tissue screening using the Myriad myChoice® HRD diagnostic test to determine eligibility.

13. Triple-Negative Breast Cancer (Expansion Cohort 2)

- a. Patients with known or suspected deleterious mutations in *BRCA1* or *BRCA2* are classified as HRD+, regardless of the molecular signature result.
 - If HRD or BRCA 1/2 mutation status is unknown or has not been previously evaluated, the patient must undergo tissue screening using the Myriad myChoice® HRD diagnostic test to determine eligibility.
- b. 0-1 prior platinum-containing treatment in any treatment setting
 - Note: Patients could have received additional therapy after the last platinum-containing regimen as long as the other eligibility criteria are met.
- c. Received ≤ 3 prior lines of therapy in the advanced or metastatic setting

14. Metastatic Castration-Resistant Prostate Cancer (Expansion Cohort 3)

- a. Patients with known or suspected deleterious mutations in *BRCA1* or *BRCA2* are classified as HRD+, regardless of the molecular signature result.
 - If HRD or *BRCA1/2* mutation status is unknown or has not been previously evaluated, the patient must undergo tissue screening using the Myriad myChoice® diagnostic test to determine eligibility.

- b. The patient may be either chemotherapy-naïve or have previously had no more than two taxane-based chemotherapy regimens including docetaxel and carbazitaxel. If docetaxel is used more than once, this will be considered as one regimen.
- c. The patient may be pre- or post-treatment with a novel androgen receptor targeted agent (e.g., abiraterone and/or enzalutamide).
- d. At least 2 weeks since the completion of prior flutamide, bicalutamide, and nilutamide, or enzalutamide and abiraterone treatment
- e. At least 2 weeks from any radiotherapy, with the exception of a single fraction of radiotherapy for the purposes of palliation (confined to one field)
- f. Documented prostate cancer progression as assessed by the investigator with one of the following:
 - Prostate-specific antigen (PSA) progression defined by a minimum of 3 rising PSA levels with an interval of ≥ 1 week between each determination. The PSA value at the screening visit should be ≥ 2 $\mu\text{g/L}$ (2 ng/ml).
 - Radiographic progression of soft tissue disease by modified RECIST v1.1 criteria
 - Surgically or medically castrated. The testosterone levels do not need to be checked as long as the patient has been on chemical castration or undergone surgical castration for > 4 months. In all cases, the luteinizing hormone-releasing hormone (LHRH) antagonist/agonist is to be continued in these patients.
 - Patients with only non-measurable bone lesions must have either progression with 2 or more new lesions or have PSA progression within the 6-week period before study drug administration.

15. Extensive Stage Small Cell Lung Cancer (Expansion Cohort 4)

- a. Received ≤ 2 prior lines of therapy

16. Gastric/Gastroesophageal Junction Cancer (Expansion Cohort 5)

- a. Received ≤ 2 prior lines of therapy

17. HRD+ Solid Tumors, Multiple Indications (Expansion Cohort 6)

- a. Patient has histologic or cytologic-confirmed advanced (metastatic and/or unresectable)
 - non-squamous non-small cell lung cancer (NSCLC)
 - squamous NSCLC
 - esophageal cancer
 - squamous head and neck cancer
 - soft-tissue sarcomas (undifferentiated pleomorphic sarcoma, leiomyosarcoma, malignant peripheral nerve sheath tumor, dedifferentiated liposarcoma, myxofibrosarcoma)

- b. Patients must have tumors with homologous recombination deficiency (HRD+) as centrally determined by the Myriad myChoice® HRD Plus assay irrespective of their known molecular signature
- c. Patients with nonsquamous NSCLC, squamous NSCLC, esophageal cancer, squamous head and neck cancer must have received at least 1 but not more than 3 prior lines of therapy.
- d. Patients with soft tissue sarcoma must have received at least 1 but no more than 3 prior lines of therapy. Treatment naïve patients may be allowed if, in the opinion of the investigator, available standard of care first line therapy is not appropriate

5.2. Exclusion Criteria

Patients will be excluded from the study for any of the following reasons:

1. Known hypersensitivity to any temozolomide (TMZ) component or to dacarbazine (DTIC)
2. Prior treatment with a PARP inhibitor
3. Received chemotherapy, biologic therapy, immunotherapy, or investigational agent within 3 weeks prior to Day 1 (or ≤ 5 half-lives, whichever is shorter) (unless otherwise noted in the Inclusion Criteria)
4. Patients who are considered to be refractory to platinum-based therapy (e.g., progressive disease at the first tumor assessment while receiving platinum treatment) (for patients in dose expansion phase only)
5. Have any unresolved acute effects of any prior therapy of Grade 2 or higher, except for AEs not constituting a safety risk by investigator judgment
6. Had a major surgical procedure, open biopsy, or significant traumatic injury ≤ 4 weeks prior to Day 1, or anticipation of need for major surgical procedure during the course of the study
 - Placement of vascular access device is not considered major surgery
7. Have other diagnosis of malignancy
 - Except for surgically excised non-melanoma skin cancer, adequately treated carcinoma in situ of the cervix, localized prostate cancer treated with curative intent, adequately treated low-stage bladder cancer, ductal carcinoma in situ treated surgically with curative intent, or a malignancy diagnosed > 2 years ago, with no current evidence of disease and no therapy ≤ 2 years prior to Day 1.
8. Patient who has received local radiotherapy of non-target lesions for local symptom control within the last 4 weeks must have recovered from any adverse effects of radiotherapy before recording baseline symptoms.
9. Have untreated leptomeningeal or brain metastasis. Patients with previously treated brain metastases are eligible if the metastases have shown no progression on brain computed tomography (CT) or magnetic resonance imaging (MRI) over at least 4 weeks, the

patients have no symptoms due to the brain metastases, and the patients have been off corticosteroids for ≥ 2 weeks.

10. Have active infection requiring systemic treatment
11. Have known human immunodeficiency virus (HIV) infection or serologic status reflecting active viral hepatitis infection as follows:
 - Patients with untreated chronic hepatitis B or chronic hepatitis B virus (HBV) carriers whose HBV DNA is > 500 IU/mL should be excluded. Note: Inactive HBsAg carriers and patients with treated and stable hepatitis B (HBV DNA < 500 IU/mL) can be enrolled. Patients receiving antivirals at screening should have been treated for > 2 weeks before the first dose of study drug(s).
12. Have any of the following cardiovascular criteria:
 - Current evidence of cardiac ischemia
 - Current symptomatic pulmonary embolism
 - Acute myocardial infarction ≤ 6 months prior to Day 1
 - Heart failure of New York Heart Association Classification III or IV ([Appendix 3](#)) ≤ 6 months prior to Day 1
 - Grade ≥ 2 ventricular arrhythmia ≤ 6 months prior to Day 1
 - Cerebral vascular accident (CVA) ≤ 6 months prior to Day 1
13. Have an active inflammatory gastrointestinal disease, chronic diarrhea, or had previous complete gastric resection or lapband surgery

Note: Gastroesophageal reflux disease under treatment with proton pump inhibitors is allowed (assuming no drug interaction potential).
14. Use or have anticipated need for food or drugs known to be strong or moderate cytochrome P450 (CYP)3A inhibitors or strong CYP3A inducers ≤ 10 days (or ≤ 5 half-lives, whichever is shorter) prior to Day 1 ([Appendix 4](#))
15. Are pregnant or nursing (females of childbearing potential require a negative serum pregnancy test ≤ 7 days before Day 1)
16. Have hereditary problems of galactose intolerance, the Lapp lactase deficiency, or glucose-galactose malabsorption

6. STUDY TREATMENT

6.1. Study Drugs

6.1.1. Pamiparib (BGB-290)

Patients will receive pamiparib as 10 mg, 20 mg, 40 mg, or 60 mg capsules, depending on dose level and capsule availability.

6.1.1.1. Packaging and Labelling

Pamiparib capsules are provided in a container with a child-resistant closure and labelled in accordance with all applicable local regulatory requirements.

6.1.1.2. Handling and Storage

The instructions for drug ordering are in the Pharmacy Binder. Pamiparib must be kept at 15-30°C. An accurate study drug accountability log must be maintained and kept up-to-date at all times.

6.1.1.3. Dosage and Administration

Pamiparib 60 mg will be administered PO BID, once in the morning and once in the evening, approximately 12 hours apart, each day for the protocol-prescribed dosing period. Pamiparib can be dosed with TMZ.

A lower dose of pamiparib or a QD regimen for pamiparib may be explored (see Section 4.2.1).

Patients will be instructed to swallow the capsules whole, in rapid succession, with water. Patients will be required to fast for at least 2 hours before and 1 hour after each pamiparib administration. Water is allowed during the fasting period.

A dose of pamiparib should be skipped if it is not taken within 2 hours of the scheduled time. An extra dose of pamiparib should not be taken to make up for a missed dose. If vomiting occurs during the course of treatment, no re-dosing of the patient is allowed before the next scheduled dose.

On days with PK assessments, pamiparib (first dose) and TMZ should be administered in the clinic.

6.1.2. Temozolomide

6.1.2.1. Packaging and Labelling

Capsules of TMZ are available in 5 mg, 20 mg, 100 mg, and 140 mg, depending on dose level and capsule availability. Please refer to the package insert for detailed information.

6.1.2.2. Handling and Storage

Please refer to the package insert for detailed information.

6.1.2.3. Dosage and Administration

Temozolomide will be administered PO QD, preferably in the morning (see dosing schedule below [Table 2](#)). TMZ can be administered with pamiparib. The daily dose and schedule will be determined as outlined in Section [4.2.1](#).

Patients will be instructed to swallow the capsules whole, in rapid succession, with water. Patients will be required to fast for at least 2 hours before and one hour after each TMZ administration. Water is allowed during the fasting period.

A dose of TMZ should be skipped if it is not taken within 2 hours of the scheduled time. An extra dose of TMZ should not be taken to make up for a missed dose. If vomiting occurs during the course of treatment, no re-dosing of the patient is allowed before the next scheduled dose.

In this study, TMZ will be administered as a flat dose rather than based on body surface area (BSA). The conversion of dose levels for TMZ for this study into BSA-based doses are as follows in [Table 2](#).

Table 2: Comparison of Temozolomide Dosing: Flat fixed versus BSA-based

Flat Dose QD	BSA Equivalent ¹
20 mg	11.5 mg/m ²
40 mg	23.0 mg/m ²
60 mg	34.7 mg/m ²
80 mg	46.0 mg/m ²
120 mg	69.0 mg/m ²

BSA = body surface area; QD = once daily

¹ Dose equivalent information is provided for reference only and assumes an average body surface area of 1.73 m²

On days with PK assessments, pamiparib and TMZ should be administered in the clinic.

6.1.2.4. Temozolomide and Pamiparib Drug-drug Interaction Potential

Temozolomide is spontaneously hydrolyzed at physiologic pH to the active species, 5-(3-methyltriazene-1-yl)-imidazole-4-carboxamide (MTIC) and to TMZ acid metabolite. MTIC is further hydrolyzed to 5-amino-imidazole-4-carboxamide (AIC), which is known to be an intermediate in purine and nucleic acid biosynthesis, and to methylhydrazine, which is believed to be the active alkylating species. Cytochrome P450 enzymes play only a minor role in the metabolism of TMZ and MTIC (USPI).

A CYP phenotyping study using human liver microsomes with selective CYP inhibitors and recombinant CYP enzymes suggests that CYP3A is the major CYP isoform responsible for pamiparib metabolism while CYP2C8 contributes to pamiparib metabolism to a lesser extent. Pamiparib is a moderate inhibitor for CYP2C9 (IC₅₀ = 6.48 μM) while its IC₅₀ for other CYP isozymes are all greater than 10 μM. Pamiparib is not a time-dependent CYP inhibitor of the 7 major CYP isozymes tested (please refer to the IB for additional information [[59](#)]).

Consequently, the drug-drug interaction potential between pamiparib and TMZ is believed to be low when co-administered.

6.1.3. Modifications of Study Drugs

6.1.3.1. General Considerations for Modifications of Study Drugs

AEs should be assessed as best as possible regarding their relatedness to one or both study drug(s). Investigators should discuss potential dose modifications with the Medical Monitor prior to implementation, if feasible. Regardless of discontinuation of one or both study drugs, patients should continue on study, with regular follow-up as outlined in Section 8.5.

Patients who experience a DLT during the DLT assessment window, or a clinically significant Grade 2 toxicity or Grade 3 or 4 toxicity considered related to study drug(s) after the DLT assessment window, may temporarily suspend study drug. Depending on the toxicity, study drug may resume within 28 days after discussion with the Medical Monitor.

Dosing of pamiparib and TMZ can be interrupted for approximately 28 days for medical events that are not associated with toxicity related to these study drugs or disease progression without discontinuing the patient from the study. If study drug is planned to be held > 28 days, the medical monitor must be contacted before permanent patient discontinuation.

Criteria for dose modifications and suggested guidelines for the management of toxicities related to pamiparib and/or TMZ are summarized below. These general guidelines may be modified at the discretion of the investigator based on best clinical judgement at that time. Any toxicities related to pamiparib and/or TMZ should be managed according to standard medical practice.

6.1.3.2. Dose Interruption and Modification of Pamiparib and Temozolomide

As discussed in Section 1.3 and Section 1.6, PARP inhibitors show at least partial overlap with the safety profile of TMZ, thus making it likely that patients in this study may experience pamiparib and TMZ-related AEs at a higher frequency and/or severity. In addition, patients may encounter AEs that are uniquely caused by the novel combination of pamiparib and TMZ.

In the context of this study, the role of TMZ is to sensitize tumor cells to pamiparib through DNA damage that can be caused by relatively low doses of TMZ. Given the favorable safety profile of pamiparib (Section 1.5), it is reasonable to assume that a Grade 3 or 4 AE is more likely to be due to the addition of TMZ to pamiparib rather than pamiparib on its own. Following this rationale, the decision of a dose reduction will affect TMZ first, and a maximum of two TMZ dose reductions are allowed.

Patients enrolled in the pulsed schedule (Arm A) who undergo AEs may re-start TMZ after the AE has recovered at the same dose or at a reduced dose as specified in Table 3, provided 3 weeks have passed from the last full TMZ dosing. For alternate scenarios, please contact the medical monitor for instructions. Pamiparib should be resumed and administered continuously at 60 mg BID, unless a dose reduction is specified.

Should TMZ dose reduction in itself be insufficient to ensure tolerability of the combination regimen, dose reductions of pamiparib in 20 mg increments may be discussed with the Medical Monitor, and a maximum of two pamiparib dose reductions is allowed. Depending on the toxicity that is triggering a second TMZ dose reduction, the possibility of a concurrent pamiparib dose reduction may be discussed with the Medical Monitor. If the blood count levels have not recovered to NCI-CTCAE Grade 1 or less after 4 weeks, further investigations should be

considered, including bone marrow analysis and blood sample for cytogenetics. If MDS or AML is confirmed, discontinue pamiparib. The criteria for dose modifications and reductions for pamiparib and TMZ are outlined in [Table 3](#).

Table 3: Criteria for Interruption and Modification of Pamiparib and Temozolomide Dosing

Worst toxicity CTCAE 4.03 Grade (value)	Recommended dose modification any time during a cycle of therapy
Hematologic	
Anemia (hemoglobin, Hgb)	
Grade 2 (Hb < 10 - 8 g/dL)	
First occurrence: continue dosing at current dose level
 
Second and subsequent occurrences: hold pamiparib and TMZ until resolved to ≤ Grade 1 or baseline
 
 • If resolved ≤ 14 days, then maintain dose levels • If resolved > 14 days, then ↓ TMZ by 1 dose level and continue pamiparib at same dose
Grade 3 (Hb < 8 g/dL)	
 • Subsequent occurrence following dose reduction for anemia: • Continue pamiparib and TMZ without interruption with appropriate supportive care based on clinical assessment OR • Hold pamiparib and TMZ and treat as medically indicated to get Hgb to ≥ 9 g/dL, then restart at reduced dose level OR • Hold pamiparib and TMZ and treat as medically indicated to get Hgb to ≥ 9 g/dL, then ↓ TMZ by 1 additional dose level
Grade 4 (life threatening consequences; urgent intervention indicated)	
 • Second occurrence following dose reduction for anemia: • Hold pamiparib and TMZ and treat as medically indicated to get Hgb to ≥ 9 g/dL, then ↓ TMZ by 1 additional dose level • Third occurrence following 2 dose reductions for anemia: • Discontinue pamiparib and TMZ if anemia is not caused by any other confounding event, e.g., gastrointestinal hemorrhage • Hold pamiparib and TMZ and treat as medically indicated to get Hgb to ≥ 9 g/dL, then restart at reduced dose level
Neutropenia (ANC)	
Grade 3 (ANC < 1.0 - 0.5 x 10 ⁹ /L)	
Hold pamiparib and TMZ until resolved to Grade ≤ 1 or baseline
 
 • If resolved ≤ 7 days, then maintain dose levels • If resolved > 7 days, then ↓ TMZ by 1 dose level
Grade 4 (ANC < 0.5 x 10 ⁹ /L)	
Hold pamiparib and TMZ until resolved to Grade ≤ 1 or baseline and ↓ TMZ by 1 dose level

Febrile neutropenia (ANC < 1.0 x 10 ⁹ /L with single temperature of > 38.3°C or sustained temperature of ≥ 38°C for > 1 hour)	
Hold pamiparib and TMZ until resolved and ↓ TMZ by 1 dose level

Table 3: Criteria for Interruption and Modification of Pamiparib and Temozolomide Dosing (Continued)

Worst toxicity CTCAE 4.03 Grade (value)	Recommended dose modification any time during a cycle of therapy
Thrombocytopenia	
Grade 3 (PLT < 50- 25 x 10 ⁹ /L)	Hold pamiparib and TMZ until resolved to Grade ≤1 or baseline 
 • If resolved ≤ 7 days, then maintain dose levels • If resolved > 7 days, then ↓ TMZ by 1 dose level
Grade 4 (PLT < 25 x 10 ⁹ /L)	Hold pamiparib and TMZ until resolved to Grade ≤ 1 or baseline and ↓ TMZ by 1 dose level
Renal	
Serum Creatinine	
2-3 x ULN	Hold BGB-290 and TMZ until resolved to Grade ≤1 or baseline 
 • If resolved ≤7 days, then maintain dose levels • If resolved >7 days, then ↓ TMZ by 1 dose level
Grade 3 (>3.0 - 6.0 x ULN) and Grade 4 (>6.0 x ULN)	Permanently discontinue pamiparib and TMZ
Hepatic	
Bilirubin	
Grade 2 (> 1.5 - 3.0 x ULN) and Grade 3 (> 3.0- 10.0 x ULN)	Hold pamiparib and TMZ until resolved to Grade ≤ 1 or baseline 
 • If resolved ≤ 7 days, then maintain dose levels • If resolved > 7 days, then ↓ pamiparib and TMZ by 1 dose level
Grade 4 (> 10.0 x ULN)	Permanently discontinue pamiparib and TMZ Note: If Grade 3 or 4 hyperbilirubinemia is due to the indirect (unconjugated) component only, and hemolysis as the etiology has been ruled out as per institutional guidelines (e.g. review of peripheral blood smear and haptoglobin determination), then ↓ pamiparib and TMZ by 1 dose level and continue study drug administration at the discretion of the investigator.
AST or ALT	
Grade 3 (> 5 and ≤ 20 x ULN)	Hold pamiparib and TMZ until AST and/or ALT resolved to ≤ 5 x ULN or baseline 
 • If ≤ 5 x ULN within 14 days, then ↓ pamiparib and TMZ by 1 dose level • If second episode, discontinue pamiparib and TMZ • If persistent for > 14 days, discontinue pamiparib and TMZ
Grade 4 (> 20 x ULN)	Permanently discontinue pamiparib and TMZ
Pancreatic	
Pancreatitis Grade 3 or 4	Permanently discontinue pamiparib and TMZ

Table 3: Criteria for Interruption and Modification of Pamiparib and Temozolomide Dosing (Continued)

Worst toxicity CTCAE 4.03 Grade (value)	Recommended dose modification any time during a cycle of therapy
Cardiac	
Cardiac - prolonged QTc interval QTcF > 500 ms or > 60 ms from the highest value at baseline or predose	
 • Obtain triplicate ECGs (5 minutes apart) ~1 hour after initial ECG • If mean QTcF > 500 ms, hold pamiparib and TMZ until evaluation of ECGs by cardiologist 
 a. Cardiology evaluation as soon as practical but within 7 days of initial abnormal ECG • If mean QTcF > 500 ms confirmed by cardiologist, discontinue pamiparib and TMZ
Cardiac general Grade 3	Hold pamiparib and TMZ until resolved to Grade ≤ 1 or baseline and ↓ TMZ 1 dose level
Grade 4	Permanently discontinue pamiparib and TMZ
Other adverse events	
Grade 3	Hold pamiparib and TMZ until resolved to Grade ≤ 1 or baseline and ↓ TMZ by 1 dose level No dose reduction required for asymptomatic laboratory abnormalities
Grade 4	Permanently discontinue pamiparib and TMZ

ALT = alanine aminotransferase; ANC = absolute neutrophil count; AST = aspartate aminotransferase; ECG = electrocardiogram; Hgb = hemoglobin; ms = milliseconds; PLT = platelet; QTc = QT interval corrected for heart rate; QTcF = QT interval corrected for heart rate using Fridericia's formula; TMZ = temozolomide; ULN = upper limit normal

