1.5.3. Clinical Safety and Preliminary Efficacy for BGB-290-AU-002

BGB-290-AU-002 is a first-in-human study evaluating pamiparib to characterize the safety, MTD, preliminary anti-tumor activity, and the PK of pamiparib given as a monotherapy in a 3+3 dose escalation scheme. Pamiparib was administered in doses ranging from 2.5 mg orally (PO) BID up to 120 mg PO BID.

The study was conducted in 5 Australian study centers and preliminary data for 45 patients are available (cut-off date of 30 September 2016).

The preliminary safety data indicate the most frequent related AEs ($\geq 10\%$ of patients) assessed as related were nausea (58%, n = 26), vomiting (51%, n = 23), fatigue (29%, n = 13), diarrhea (18%, n=8), dry mouth (16%, n=7), and decreased appetite (11%, n=5). Hematologic AEs, regardless of relatedness, were reported in 40% of patients (n=18). Anemia was most frequent (33%, n=15), followed by neutropenia (11%, n=5) and thrombocytopenia (2%, n=1).

Twenty-six percent of the patients experienced a Grade 3 AEs (regardless of relatedness), and no Grade 4 AEs were reported. Eleven Grade 3 AEs in 9 patients (20%) were considered related to BGB-290: anemia (n=5), neutropenia (n=3), hypophosphatemia (n=1), nausea (n=1), and fatigue (n=1). Serious AEs reported as related to BGB-290 included anemia (n=2) and nausea (n=1).

The DLT of BGB-290 was persistent Grade 2 nausea despite optimal standard medical therapy observed in the 120 mg BID cohort (n=2) and in one patient each in the 40 mg and 80 mg BID cohorts. The MTD of BGB-290 was 80 mg PO BID.

Ten patients achieved either complete (n=2) or partial (n=8) responses; all responses were observed in patients with gynecological cancers, and responses were observed in the lowest dose cohorts (2.5 mg BID).

Based upon the overall safety, efficacy, and PK profile of pamiparib, the dose for further investigation was determined to be 60 mg PO BID.

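### In Table 3 of the protocol, the least strict recommended action for anemia and the hemoglobin level that ends a hold are both looser at Grade 3 than at repeat Grade 2.

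*Protocol*

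**What the plan says.** The anemia rows of Table 3 (Protocol Section 6.1.3.2) read as follows.

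- **Grade 2, hemoglobin 8 to below 10 g/dL.** "First occurrence: continue dosing at current dose level". After that: "Second and subsequent occurrences: hold pamiparib and TMZ until resolved to ≤ Grade 1 or baseline". If the event resolves within 14 days, dose levels are kept; if it takes longer, TMZ drops one level.
- **Grade 3, hemoglobin below 8 g/dL.** Under the line "Subsequent occurrence following dose reduction for anemia" stand three alternatives joined by OR. The first is "Continue pamiparib and TMZ without interruption with appropriate supportive care based on clinical assessment OR". The other two are holds until hemoglobin reaches 9 g/dL, followed by a reduced dose.
- **Grade 4.** The holds listed also end at 9 g/dL and lead to a reduced dose. The third occurrence after two reductions leads to discontinuation unless another event explains the anemia.

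The table's first column is keyed to the worst grade reached, and its second is headed as a recommendation. Section 6.1.3.1 describes the criteria as suggested guidelines that the investigator may modify, and asks that dose changes be discussed with the Medical Monitor where feasible.

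**The concern.** A dose-modification table normally becomes no more permissive as toxicity worsens. Here, a patient with a repeat event at 8.5 g/dL is to be held, but if the same event falls below 8 g/dL, uninterrupted dosing becomes a listed choice. No reason is given.

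Safety and tolerability are primary objectives. Exposure, dose intensity, reductions and interruptions are planned outputs (Protocol Section 11.3.1; SAP Section 6.4.1). If sites resolve the rows differently, these outputs partly reflect local reading of the table, and patients with the same hemoglobin are managed differently.

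There is also a possible route into dose finding. Grade 3 anemia is not a DLT (only Grade 4 is, Section 4.2.4), and patients who receive less than 70% of scheduled dosing in Cycle 1 are not evaluable and may be replaced (Section 4.2.3). For a drug given daily over 28 days, 30% is 0.30 × 28 = 8.4 days. A longer hold in Cycle 1 can therefore remove a patient whom the continue option would have kept. This route is narrow if the Grade 3 options apply, as printed, only to a recurrence after a dose reduction.

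**Working it through.** The plan states no figure to reproduce, so the check sets the rows side by side.

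| | Repeat Grade 2 | Grade 3 | Grade 4 |
|---|---|---|---|
| Hemoglobin (g/dL) | 8 to < 10 | < 8 | defined clinically |
| Least strict action listed | hold both drugs | continue both, uninterrupted | hold both drugs |
| Hold ends at | Grade 1 or baseline | ≥ 9 g/dL | ≥ 9 g/dL |
| Dose after hold | same if ≤ 14 days, else TMZ down one level | reduced | reduced |

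**Action.** At repeat Grade 2 the only listed action is a hold. At Grade 3 the set is continue, hold or hold. The minimum is lower at Grade 3.

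**Restart level.** By the table's own range, Grade 2 begins below 10 g/dL, so resolution to Grade 1 means at least 10 g/dL. Inclusion criterion 7c (Section 5.1) requires at least 10 g/dL at screening, so the baseline alternative will not ordinarily be lower. Grade 3 and 4 holds end at 9 g/dL. The difference is 10 − 9 = 1 g/dL. A patient at 9.5 g/dL may restart after Grade 3 but stays on hold after a repeat Grade 2, and the table does not say whether that 9.5 g/dL then counts as a new Grade 2 occurrence.

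**Sensitivity to bullet order.** Text extraction may have moved bullets within or between the Grade 3 and Grade 4 cells.
- If the continue option belongs where it is printed, it applies to a Grade 3 recurrence in a patient already reduced for anemia.
- If it belongs to a first Grade 3 event, the comparison is less like for like, because a first Grade 2 event also continues. Grade 3 still permits what repeat Grade 2 does not.
- If it belongs to Grade 4, the contrast is larger.
- The 9 g/dL level appears in every hold in both cells, so its position does not matter.

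**Other Grade 3 rows.** Neutropenia and thrombocytopenia are held, with no option to continue. The table's explicit allowance to continue for indirect hyperbilirubinemia comes with a reduction of both drugs. The anemia row lists continuation with neither interruption nor reduction.

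**Frequency in the protocol's own data (Section 1.5.3).** Anemia of any relation: 15/45 = 33% of patients. Related Grade 3 events: 5 + 3 + 1 + 1 + 1 = 11, in 9 patients, so the counts listed by type are events. At most 11 − 9 = 2 of the anemia events can be repeats in the same patient, so 5 − 2 = 3 to 5 patients had related Grade 3 anemia, which is 3/45 = 7% to 5/45 = 11%.

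**The case against.** The strongest reply is that nothing here is compulsory. The column is headed as a recommendation, Section 6.1.3.1 gives the investigator discretion, and two of the three Grade 3 alternatives are holds. Those holds are stricter than the Grade 2 hold in one respect: both lead to a reduced dose, whereas a Grade 2 hold of 14 days or less does not. SAP Section 8 adds a summary of reasons for reductions, interruptions and missed doses, so some of the resulting variation would be visible.

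All of this stands, and it limits the point. It does not answer it: discretion allows departure from a default, but the default should still be coherent across grades.

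Three stronger readings are tempting, and the documents do not support them.

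- *One episode receives opposite instructions, or the rows cannot all be followed.* The table is keyed to worst toxicity, so an episode that reaches Grade 3 is handled in the Grade 3 row. An investigator who holds at both grades is consistent with both rows.
- *The plan gives no instruction for a first Grade 3 anemia.* None is legible, but the bullets in the Grade 3 and Grade 4 cells may have been displaced in extraction, so the gap cannot be charged to the plan on this text.
- *About 28 of 250 patients would fall into the row.* That applies 5/45 to the enrollment ceiling. It treats events as patients, uses monotherapy at doses from 2.5 to 120 mg BID, and ignores that the row as printed covers only recurrences after a dose reduction.

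**Conclusion.** The point holds as an internal inconsistency in recommended management. For anemia, the mildest listed action and the hemoglobin level for restarting are both looser above Grade 2 than at repeat Grade 2, except that the Grade 4 row differs only in the restart level. The conclusion rests on the Grade 2 cell being legible as printed and on the continue option belonging to Grade 3 or Grade 4; it does not depend on the order of bullets within those cells.

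Its size in this study cannot be derived. The documents show only that anemia was the most frequent hematologic event with pamiparib alone (33%) and that 3 to 5 of 45 patients had related Grade 3 anemia. The protocol expects overlapping toxicity with TMZ to be more frequent or severe, but gives no rate for the combination. The matter bears on patient safety and on how exposure results are read, and it is cheap to correct.

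**What to change.** The sponsor's clinical team should reconcile the Grade 2, 3 and 4 anemia rows of Table 3 with each other. Three items need settling: which continue or hold options apply at each grade, the hemoglobin level at which dosing may restart after a hold, and which occurrence each instruction refers to, including whether a value between 9 and 10 g/dL after restart counts as a new Grade 2 event. If the contrast is intended, a sentence giving the reason would do. The choice of rule is the sponsor's, and none is proposed here.

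The cost is rewording three table rows in a protocol amendment, with no added visits, tests or procedures.
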